4.5 Study Evaluations

Our primary evaluation measures for this feasibility trial will be measures of feasibility, acceptability, and adherence. Our secondary measures will be administered to pilot the administration of psychometric measures for future trials. Evaluations will be conducted during two baseline sessions (prior to randomization), at post-treatment (12-week evaluation), and (for Phase Two only) at 3-month follow-up (24-week evaluation). A VA approved videoconferencing platform (e.g., Cisco Webex, Microsoft Teams) will be used to administer the measures that need to be conducted by staff (see below). Study staff will also instruct participants regarding how to complete the questionnaires collected electronically using the Qualtrics program and will be available to answer participants' questions in order to facilitate completion. Post-treatment and 3-month follow-up assessments will be completed in one or two sessions.

In order for the baseline data to be valid, the baseline assessment should be completed within approximately one month prior to group assignment. The sit to stand task (planned to be administered at the first baseline session) may be readministered closer to the group start date if delays have taken place. Also, if participants were unable to complete the sit to stand task at the first baseline assessment (e.g. if they do not have an appropriate chair available), it may be completed later.

A. Primary Measures: Feasibility and Acceptability, Measures of Participant Satisfaction and Adherence	
Measure	Description, Citation, and Metric for Current Study
The Client Satisfaction Questionnaire (CSQ)	
The CSQ assesses participants satisfaction with patient care³⁹. Administered at post-treatment, and 3-month follow-up (for Phase Two only) via Qualtrics. There are 8 original items that focus on client satisfaction and 3 supplementary items that measure global life satisfaction, general health status and global effectiveness of services received.
 
Metric: At least 70% of participants will have a mean item-score of 3 or greater on the 1-4 scale of the 8 original items at post-treatment.

Participant Adherence Attendance/Compliance	
Study staff will monitor number of missed sessions, reasons given for missing sessions, and completion of assessments.
 
Metric: 75% of participants will attend at least 70% of the treatment sessions. 70% of participants will complete all assessments (baseline through follow-up).

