Credibility/Expectancy Questionnaire (CEQ).	
Assesses participants' perceptions of treatment credibility and outcome expectancy in clinical outcome trials.⁴¹
 
Administered at weeks 1,2,4, and 9 via Qualtrics
 
Metric: At least 70% of participants will report a mean item-score of 6 or greater on the 1-9 scale by week 4 for both credibility and expectancy

Weekly Log Sheets	
Participants will keep logs of homework/practice that will be reported via telephone to the project coordinator weekly during the 12-week intervention period. In the Tai Chi condition, they will record the number of minutes per day spent on home practice. In the Wellness condition, they will record weekly goals.
 
Metric: At least 75% of participants will complete at least 70% of weekly log sheets.

B. Secondary Measures Outcome Measures to Be Administered to Ascertain Burden and Calculate Intra-Class Correlation Coefficients	
Administered at baseline, post-treatment (12-weeks), and 3-month follow-up (24-weeks), for Phase Two only (Note that CAPS-5 will only be administered at baseline and post-treatment for Phase Two)	
Construct and Measure	Description and Citation
PTSD severity: Clinician Administered PTSD Scale – 5th Edition (CAPS-5)	The CAPS-5 is a structured diagnostic interview for PTSD administered by study staff. ⁴² The interviews will take place using a VA approved platform (e.g., Cisco Webex or Microsoft Teams). During Phase Two , this diagnostic interview will be video-recorded, with participant permission and administered at baseline and post-treatment. The recordings will be used to ensure reliability of assessor ratings.
Pain: The Brief Pain Inventory – Short Form (BPI)	The BPI is a self-report measure that examines pain intensity and interference with functioning in various life domains. ^{43,44} Administered via Qualtrics. ^{43, 44}
Medical Outcomes Study Self-Reported Measure of Health Status: 36-Item Short Form Survey (SF-36)	The SF-36 is a 36 item self-report questionnaire that assesses self-perception of health status in the following domains: physical functioning, role limitations due to physical and emotional factors, social functioning, bodily pain, general health, vitality, and mental health. ⁴⁵ Administered via Qualtrics.

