Physical Functioning: 30 second Sit to Stand Test (30-s STS)	The 30-s STS is an objective measure of lower body strength. ⁴⁶ Administered by study staff over videoconference platform.
---	---

C. Weekly Outcome Measures to Be Administered to Ascertain Burden

Administered weekly using Qualtrics throughout intervention period (both *Phase One* and *Phase Two*)

Construct and Measure	Description and Citation
PTSD: The PTSD Checklist for DSM-5 (PCL-5)	The PCL-5 is a 20-item self-report measure that examines symptoms of DSM-5 posttraumatic stress disorder criteria over the past week. ^{47,48} Administered via Qualtrics.
Pain: The Brief Pain Inventory – Short Form (BPI)	In addition to being administered at the primary assessment points (baseline, post-treatment, 3-month follow-up) as noted above, the BPI will be administered weekly during the intervention period using Qualtrics. ^{43, 44 43,44}

D. Other Descriptive Measures

Demographics	This information will be used to provide a comprehensive description of the sample of Veterans and variables may be used as covariates in sensitivity analyses. Administered at baseline. Administered via Qualtrics.
Life Events Checklist Extended Self Report	The LEC-5 will be used to establish Criterion A for the CAPS-5 interview with study staff. Administered at baseline. Administered via Qualtrics.
Psychoactive and Pain Medication Usage	A list of current, prescribed psychoactive and pain medications will be obtained through VA electronic medical record and verified through participant self-report at baseline and updated at subsequent assessments. For each prescribed medication, staff will ask whether participants have been taking medications as prescribed during the previous period and will document lapses and changes.

E. Other Measures

Telephone Screening Form	Potential participants will be screened over the telephone by study staff to determine if they meet inclusion criteria. Individuals who meet this initial criteria will be scheduled for the baseline assessment where the Informed Consent will be reviewed and signed.

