- Credibility will be measured by the CEQ with at least 70% of participants reporting a credibility rating of 6 or greater on the 9-point scale.
- Compliance with home practice will be measured by 75% of participants completing 70% of weekly log sheets.

Measures to be examined for participant burden for the larger trial will assess PTSD symptom severity, pain levels, global health, and physical functioning at baseline, post-treatment and (for *Phase Two* only) 3-month follow-up. In the qualitative feedback interviews, we will further assess these issues to determine if changes are needed regarding recruitment, retention, adherence, and participant burden. If we do not meet the feasibility goals, we will reevaluate to make refinements before developing protocols for a future large trial.

AIM 3. We will utilize information from this trial to plan and design a large, randomized control study evaluating the efficacy of Tai Chi compared to Wellness for improving outcomes for Veterans with PTSD and chronic musculoskeletal pain.

The Tai Chi and Wellness control protocols developed, revised, and finalized as part of the proposed project will be used in a future larger study designed to evaluate Tai Chi for PTSD and chronic pain. The current study will provide preliminary data on feasibility, acceptability, adherence, and participant burden. In addition, the preliminary trial will allow us to work out technology issues to optimize our use of remote videoconferencing and to develop methods to maximize efficiency for research staff that will help guide the design of this large-scale trial. If we fall short of recruitment and/or retention goals, we will use the information gathered during the qualitative interviews and study staff experience to make further refinements to our remote protocol (e.g. providing additional resources for assistance with technology issues for participants, providing videocams or tablets to all participants, assistance with home setup, etc.).

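### Section 4.7 lists PTSD severity among the constructs assessed at the 3-month follow-up, but section 4.5 schedules no PTSD measure at week 24

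*Combined protocol and SAP*

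**What the plan says.** Section 4.7, under Aim 2, describes the measures to be examined for burden with the larger trial in mind. They "will assess PTSD symptom severity, pain levels, global health, and physical functioning at baseline, post-treatment and", for Phase Two, the 3-month follow-up.

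Section 4.5 gives the schedule instrument by instrument:

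- **Table B, general line:** "Administered at baseline, post-treatment (12-weeks), and 3-month follow-up (24-weeks), for" Phase Two. This covers the BPI, SF-36 and 30-second sit to stand test.
- **Table B, exception in the same heading:** "Note that CAPS-5 will only be administered at baseline and post-treatment for" Phase Two. The CAPS-5 row repeats it: "this diagnostic interview will be video-recorded, with participant permission and administered at baseline and post-treatment".
- **Table C, which holds the PCL-5:** "Administered weekly using Qualtrics throughout intervention period". The PCL-5 row says that it "examines symptoms of DSM-5 posttraumatic stress disorder criteria over the past week" and adds no other occasion.
- **Table C, BPI row:** "In addition to being administered at the primary assessment points (baseline, post-treatment, 3-month follow-up) as noted above", the BPI is also given weekly.

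The opening of section 4.5 gives the purpose of the secondary measures: "Our secondary measures will be administered to pilot the administration of psychometric measures for future trials".

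**The concern.** The two sections disagree about what is collected at week 24, and the construct left out is one of the two conditions that define the trial population. If staff follow 4.5 exactly, an assessment stated in 4.7 does not take place.

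The secondary measures are there to pilot instruments, and table B is headed as serving burden and intra-class correlation (ICC). Aim 3 is to plan an efficacy trial in Veterans with PTSD and chronic musculoskeletal pain. As scheduled, completion, burden and variability at the follow-up visit can be examined for pain, health status and physical functioning, but not for PTSD. Week-24 scores cannot be collected afterwards.

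**Working it through.** The plan states no figure to reproduce on this point, so the check sets the section 4.5 schedule against the list in section 4.7.

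**1. Coverage in Phase Two**

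| Construct in 4.7 | Instrument in 4.5 | Baseline | Week 12 | Week 24 |
|---|---|---|---|---|
| Pain | BPI | yes | yes | yes |
| Global health | SF-36 | yes | yes | yes |
| Physical functioning | 30-s STS | yes | yes | yes |
| PTSD severity | CAPS-5 | yes | yes | **no** |
| PTSD severity | PCL-5 | no | weekly during intervention | **no** |

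The Life Events Checklist (table D) is given at baseline only, to establish Criterion A, and is not a severity scale. The SF-36 mental health domain is a general health-status score. The CSQ, the feedback items and interview, and the PHI do not measure PTSD. Coverage at week 24 is therefore 3 of 4 constructs.

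**2. Other readings of the CAPS-5 note.** It could mean that the post-treatment interview is for Phase Two only. No reading places a CAPS-5 at week 24.

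**3. Whether the weekly forms run past week 12.** The payments in section 4.3 give a test. Assume 24 sessions (twice weekly for 12 weeks), 12 weekly calls and 12 weekly measure sets:

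- Phase One: 2 × $25 + $65 + 24 × $5 + 12 × $5 + 12 × $5 = $355, the stated total.
- Phase Two: $355 + $80 for the follow-up = $435, the stated total.

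Twelve weekly sets account for the totals exactly. Nothing is left over for weekly forms after the intervention.

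**4. Gap.** 24 − 12 = 12 weeks from the last scheduled PTSD score to the follow-up visit. The PCL-5 looks back one week, so a week-12 score says nothing about week 24.

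**5. Counts.** At the target of 36: 0 PTSD scores at week 24, against up to 36 for each other construct. Section 4.2 allows up to 60 in Phase Two, but the PTSD count stays at 0.

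**6. Load of one added PCL-5 (20 items)**

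- Against the weekly PCL-5 total: 20 / (12 × 20) = 20/240 = 8.3%.
- Against the follow-up self-report items with a stated count, SF-36 36 + CSQ (8 + 3) = 47: 20/47 = 42.6%.
- In the Wellness arm, with the 12-item PHI, 47 + 12 = 59: 20/59 = 33.9%.

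The last two are upper bounds, because the BPI and the additional feedback items have no stated count.

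**7. What a week-24 ICC could show.** Take six groups of six, three per arm, pooled within arm, with no attrition: 4 and 30 degrees of freedom. With F = (1 + 5·ICC)/(1 − ICC), an assumed observed ICC of 0.05 gives F = 1.25/0.95 = 1.316. The 95% limits for F are 1.316/3.25 = 0.405 and 1.316 × 8.46 = 11.13. Converting by (F − 1)/(F + 5) gives an interval of about −0.11 to 0.63. For observed values of 0.01 to 0.10 the upper limit runs from 0.57 to 0.69.

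**The case against.** The strongest reply is that the schedule is clear and 4.7 is only a summary. The CAPS-5 limit is stated twice and looks deliberate, and a specific exception would normally govern a general sentence that omits it. No aim, feasibility metric or analysis calls for a week-24 PTSD score, and the documents do not say that the future trial will measure PTSD at 24 weeks. On this view one clause in 4.7 needs correcting, and adding a form is a design preference.

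Much of this is fair. The limit does look intended, and correcting 4.7 would remove the contradiction. But a limit on the interview does not explain why no self-report form takes its place, when the neighbouring BPI row extends that form to the follow-up visit. Correcting the text alone also leaves the planning gap.

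Three further points:

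- **Precision.** A week-24 ICC would be very imprecise. This stands, so the case for the added form rests on completion and burden more than on the ICC. A week-12 CAPS-5 ICC is available either way.
- **No baseline PCL-5.** It is true that one added form gives no same-instrument change from baseline. It can still be compared with the weekly PCL-5 scores, so it is not an isolated value.
- **Burden.** The relevant load is that of the follow-up visit, not the 12-week total. Completion of all assessments is a primary metric with a 70% threshold, so the added length should be weighed against it.

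**Conclusion.** The concern holds. Sections 4.5 and 4.7 contradict each other on PTSD severity at the 3-month follow-up, and under every reading of 4.5 no PTSD severity score is collected there.

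The consequence is limited. The primary feasibility and acceptability metrics, the burden of the PTSD instruments up to week 12 and a week-12 CAPS-5 ICC are untouched. No analysis specified in this trial is lost. The loss is to planning the larger trial, which would have follow-up experience with measures of pain, health status and function but none with a PTSD measure. The sponsor should resolve this before the Phase Two follow-up visits.

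The conclusion rests on the schedule as printed and on weekly forms ending with the 12-week intervention, which the payment totals support.

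**What to change.** **Preferred.** In section 4.5, add one administration of the existing Qualtrics PCL-5 to the Phase Two 3-month follow-up and leave the CAPS-5 as scheduled. In section 4.7, name the instrument that supplies PTSD severity at each visit. A PCL-5 before randomisation is optional, and is needed only if a same-instrument change score is wanted.

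**Alternative.** If no PTSD measure is wanted at week 24, remove PTSD severity from the follow-up statement in 4.7 and say that it is not piloted at that visit.

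**Cost.** The preferred change needs an IRB amendment and adds 20 items at one visit, a few minutes per participant (assumed), with no extra assessor interview. The form is already built and participants know it. The alternative is a text correction in 4.7 only.

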Feedback Interview Form	Semi-structured interview developed to obtain feedback from each participant about their participation in the study. This feedback will be obtained through interviews that will take place at post-treatment (12-weeks) and, in Phase Two, at 3-month follow-up (24-week evaluation). Interviews will take place using a VA approved platform (e.g., Cisco Webex or Microsoft Teams), and with participant permission, will be video recorded and transcribed.
Additional Feedback Questions	Some additional satisfaction items will be administered via Qualtrics to address participants' response to the specific interventions used in this study.

Personal Health Inventory (PHI)	The PHI is a 12-item self-report measure that assesses participants' relationship with 8 areas of health and well-being from the VA Whole Health Circle (model that is used in the Wellness Intervention) including relationships, sleep, exercise, food and drink, personal development, spirituality, surroundings, and power of the mind. ⁴⁹ This scale will be administered using Qualtrics to participants who are in the Wellness Intervention to measure potential growth across these 8 areas of self-care over the course of the study. It will be administered during the intervention at week 2 and week 12 in Phase 1 , and also at the 3-month follow-up (24-weeks) in Phase 2 .
---------------------------------	--

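### The PHI is first given in week 2 of the Wellness programme, so it can show change from week 2 but not growth from before treatment (minor)

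*Combined protocol and SAP*

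**What the plan says.** The PHI is described in section 4.5, table E (Other Measures). It is a 12-item self-report scale covering eight areas of health and well-being, and it goes to one arm only: "This scale will be administered using Qualtrics to participants who are in the Wellness Intervention". Its purpose is "to measure potential growth across these 8 areas of self-care over the course of the study". Its timing is "It will be administered during the intervention at week 2 and week 12", with a further form at the 24-week follow-up in Phase Two. No baseline PHI appears in tables A to E or in the text of section 4.5.

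The PCL-5 appears only in table C of the same section, headed "C. Weekly Outcome Measures to Be Administered to Ascertain Burden". It is "Administered weekly using Qualtrics throughout intervention period", and it "examines symptoms of DSM-5 posttraumatic stress disorder criteria over the past week". The Brief Pain Inventory (BPI) is in the same table, but its entry says: "In addition to being administered at the primary assessment points (baseline, post-treatment, 3-month follow-up) as noted above, the BPI will be administered weekly". The PCL-5 entry has no matching statement, and the scale is not among the baseline measures in table B or table D.

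The baseline evaluations take place before randomization (section 4.5). In Phase Two, participants are then telephoned with their assignment (section 4.6). For both interventions, staff hold a technology session with participants before the first group session (section 4.1).

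**The concern.** The PHI's stated purpose and its schedule do not match. Growth over the whole study needs a starting value from before the intervention. As written, the first score follows one to two weeks of a programme that covers much of what the scale asks about. Section 4.1 lists Wellness modules on physical activity, eating and drinking, relationships, surroundings, personal development and spirituality, and has participants set goals every week. Any early gain is absorbed into the reference value, so the week 2 to week 12 difference would tend to understate growth if participants improve early.

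What is at stake is how one descriptive measure in one arm is interpreted.

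The PCL-5 raises a weaker version of the same question. In Phase Two, any form completed in the intervention period comes after allocation is known, so the weekly series has no pre-randomization anchor. The weekly BPI series has one.

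**Working it through.** The protocol states no figure on this point, so there is none to reproduce. The check is a reading of the schedule plus simple arithmetic.

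**Inputs**
- Session frequency: twice a week for 12 weeks (section 4.7, Sample Size Calculation).
- First PHI: week 2; the day within the week is not stated (section 4.5, table E).
- Last PHI in the intervention period: week 12, taken here as the end of the programme (assumption).

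**Sessions scheduled before the first PHI**
- Total sessions: 2 × 12 = 24.
- PHI at the start of week 2: 2 × 1 = 2 sessions, and 2/24 = 8.3%.
- PHI at the end of week 2: 2 × 2 = 4 sessions, and 4/24 = 16.7%.

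**Share of 12-week growth missed**

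If a fraction *f* of the 12-week change has occurred by the first PHI, the week 2 to week 12 difference captures 1 − *f*. The documents give no time course, so *f* has to be assumed. Under linear change, *f* = (weeks elapsed)/12:
- Start of week 2: *f* = 1/12 = 8.3%, captured 11/12 = 91.7%.
- End of week 2: *f* = 2/12 = 16.7%, captured 10/12 = 83.3%.

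If gains come early, *f* is larger than this. If they come late, it is smaller.

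**Schedule of the three scales, from section 4.5**

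| Scale | Pre-randomization | During intervention | Post-treatment visit | 24 weeks (Phase Two) | Stated purpose |
|---|---|---|---|---|---|
| PHI | none | weeks 2 and 12 | none separate from week 12 | yes | growth over the study, Wellness arm |
| PCL-5 | none | weekly | none listed | none listed | burden |
| BPI | yes | weekly | yes | yes | burden; also intra-class correlation, through table B |

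For the PHI, the stated purpose calls for a starting value that the schedule does not provide. For the PCL-5, a pre-randomization value is absent but no stated purpose calls for one. The weekly wording does not place the first PCL-5 form before or after session 1.

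**The case against.** The strongest reply is that very little depends on this. The PHI is listed under other measures, goes to one arm, enters none of the feasibility or acceptability metrics in sections 4.5 and 4.7, and has no analysis in section 4.7. The text speaks only of potential growth, and change from week 2 onward remains measurable. Section 4.1 also gives no order for the Whole Health modules, so how much relevant content has been delivered by week 2 is unknown. All of this stands and sets the severity. It does not remove the mismatch between the stated purpose and the first administration.

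A reader might infer more than the documents support, in three ways.

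- **That the PHI cannot measure growth at all.** It can, from week 2 to week 12 and on to week 24 in Phase Two. Only growth from before treatment is out of reach.
- **That the PCL-5 has no pre-treatment value because it starts after the intervention has begun.** The protocol does not say so. A week-1 form completed before session 1, with its past-week recall, would describe the pre-treatment state. What is certain is narrower: no PCL-5 is scheduled before randomization, and the timing of the first form is not stated.
- **That Aim 3 fails without a PCL-5 baseline mean, SD and correlation.** Section 4.7 lists what the study is to supply for the larger trial: preliminary data on feasibility, acceptability, adherence and burden, plus lessons on technology and staff efficiency. It names no PCL-5 variance inputs and plans no PCL-5 change analysis. The CAPS-5, given at baseline and post-treatment, supplies the pre-randomization value for PTSD severity.

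There is also a fair objection to one remedy. A PHI placed in the baseline battery would precede randomization in Phase Two and so would go to future Tai Chi participants, although the protocol restricts the scale to Wellness.

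**Conclusion.** The PHI point holds, and it is minor. As scheduled, the scale has no pre-treatment value, and about 2 to 4 of 24 sessions (8% to 17%) come before its first score. Under the linear assumption, a similar share of the 12-week growth is missed. The true share depends on a time course that the documents do not give, and on when in week 2 the form is completed.

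The PCL-5 point is secondary and optional. It is a missed opportunity to anchor the weekly series before randomization, as the BPI series already is, and it contradicts no stated aim.

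No primary feasibility or acceptability conclusion is affected by either.

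**What to change.** **PHI.** Give Wellness participants the first PHI after assignment and before the first Wellness session. The technology session in section 4.1 is a ready slot and keeps the scale out of the Tai Chi arm. Keep week 12 and the Phase Two 24-week form, and define growth as change from the pre-session score. The cost is an edit to table E and a 12-item electronic form moved one to two weeks earlier. If the team also uses the week-2 form as session material (the protocol does not say), it can stay as an extra point. The minimum alternative is to reword the purpose as change from week 2.

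**PCL-5 (optional).** Add the 20-item form to the existing Qualtrics baseline, at the cost of a few minutes of baseline burden. The team may reasonably decline, since the CAPS-5 already covers PTSD severity at baseline. In either case, add one sentence to table C saying whether the first weekly form is completed before or after session 1.
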